6.4.2 Analysis of ORR (Primary)

Overall response rate (ORR) will be estimated by the percentage of patients who achieve CR, PR or SD by RECIST criteria (detailed in Sections 5.1.2.5 and 9.2), with corresponding exact 95% confidence limits being reported. The difference between marker value groups will be examined with Fisher's exact tests.

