6.3 Sample Size and Accrual

The null hypothesis that the true ORR is 10% will be tested versus a one-sided alternative of 25% or higher, using Simon's minimax two-stage design. In the first stage, 16 patients will be accrued. If there are <2 responses, the study will be stopped and alternative doses of axitinib considered. If at least 2 responses are observed, 15 additional patients will be enrolled in the 2nd stage. The combination therapy will be regarded as worthy of further study if ≥6 responses are observed in both stages. Total sample size is 31 patients. This design has a type I error rate of 0.08 with a power of 0.81 when the true response rate is 0.25. Secondary endpoints of this study are PFS, OS and safety. Survival endpoints (PFS and OS) will be estimated with the Kaplan-Meier method, and compared between marker value groups with the log-rank test. We will also perform extensive correlative analysis (flow, IHC, metabolic analyses).

The accrual rate of the trial is estimated to be 1-2 patients/month, therefore, we will be able to finish the accrual of the study in approximately 24 months.

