6.4.5 Correlative Translational Assays (Secondary)

Multiple lab outcomes will be compared between baseline and on treatment to examine the change in TME, metabolic profiling and cell hypoxia. These will also be compared between baseline and the value at the progression for progressors. All these pre vs post comparisons will be done with paired t-tests or Wilcoxon signed rank tests where appropriate. The change from pre- to post- treatment will be compared between subgroups (such as between responders and non-responders) with two sample t-test or Wilcoxon rank sum test where appropriate. The association of clinical response with tumor metabolism and with T cell function will be explored with logistic regressions. The association of survival endpoints (DOR, PFS, OS) with tumor metabolism and with T cell function will be explored with Cox proportional hazards models.

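### Hypoxia and immune-phenotype marker levels are linked to response, PFS and OS only through undefined value groups; for quantitative markers, uncut analyses of the same data would have clearly more power and leave no cut-point open

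*Combined protocol and SAP*

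**What the plan says.** Section 6.4.2, on the primary response analysis, adds: "The difference between marker value groups will be examined with Fisher's exact tests". Section 6.3 says that PFS and OS will be "compared between marker value groups with the log-rank test". Section 6.4.4 repeats a log-rank comparison between unnamed subgroups, if there are enough events. None of these sections names a marker, gives the number of groups or a cut-point, or says that cuts are fixed in advance.

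Section 6.4.5 goes further for some markers. It states: "The association of clinical response with tumor metabolism and with T cell function will be explored with logistic regressions". It plans Cox models for DOR, PFS and OS on the same two domains. It also compares TME, metabolic and hypoxia measures before and during treatment by paired tests. The change is then compared between subgroups, with responders versus non-responders as the example, by two-sample t or rank-sum test. It does not say whether markers enter the regression models as continuous values.

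Section 2.4 lists four correlative domains (hypoxia, TIL function, immune phenotype, tumor cell metabolism) and calls this work exploratory, although Section 6.4.5 is headed as secondary.

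**The concern.** Most readouts in Section 3.2.3.2 are quantitative: flow cytometry, hypoxia-related staining, cytokine production and Seahorse metabolism. Grouping such a value requires a cut, and a cut discards information. Two of the four domains in Section 2.4, hypoxia and immune phenotype, are not named in the regression models of Section 6.4.5. For their level against response, and for any relation to PFS or OS, the grouped tests are the only stated method.

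That matters in a trial this small. Section 6.3 says: "Total sample size is 31 patients". Inclusion criterion 6 in Section 4.1.1 does not require biopsiable disease, so fewer patients may have tissue markers. A real association could easily be missed. And because no cut is fixed, one could be picked after the outcomes are known, in which case a nominal 5% p-value would no longer mean 5%.

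**Working it through.** **The plan's own figures.** Section 6.3 tests a response rate of 10% against 25%, one-sided. Sixteen patients enter first; the trial ends there with 0 or 1 response and otherwise takes 15 more. Success needs at least 6 responses in 31. The probability of success is the sum over x = 2 to 16 of P(X1 = x) × P(X2 ≥ 6 − x), with X1 ~ Bin(16, p) and X2 ~ Bin(15, p).
- p = 0.10: 0.0788, stated as 0.08.
- p = 0.25: 0.805, stated as 0.81.

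The design reproduces, and no marker test enters it. The plan states no error rate, power or effect size for any marker test, so the inputs below are assumptions.

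**Assumptions.** One standard normal marker; two-sided 5% tests; 31 patients, or 20 as an assumed biopsied subset; 25% response, with 10% as a second case; effects per SD as shown. All results are from simulation, so the last digit moves between runs.

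**Response: median split with Fisher's test against rank-sum, 25% response.** Relative loss = 1 − (Fisher power ÷ rank-sum power).

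| n | Odds ratio per SD | Fisher | Rank-sum | Loss |
|---|---|---|---|---|
| 31 | 3 | 0.36 | 0.58 | 1 − 0.36/0.58 = 38% |
| 31 | 4 | 0.50 | 0.75 | 1 − 0.50/0.75 = 33% |
| 20 | 3 | 0.12 | 0.37 | 1 − 0.12/0.37 = 68% |
| 20 | 4 | 0.16 | 0.49 | 1 − 0.16/0.49 = 67% |

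With 31 patients, the side of the split on which the middle patient falls matters. The less favourable side gives Fisher power of 0.30 and 0.43, and losses of 48% and 42%. Part of the loss is Fisher's own conservatism: with a fixed median split at n = 31 and 25% response its actual size is about 2.9%.

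**PFS and OS: median-split log-rank against a Cox score test on the continuous marker, n = 31.**

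| Events | Hazard ratio per SD | Log-rank | Cox | Loss |
|---|---|---|---|---|
| 31 | 1.5 | 0.37 | 0.54 | 31% |
| 31 | 1.75 | 0.56 | 0.78 | 29% |
| 31 | 2 | 0.71 | 0.90 | 21% |
| about 23 | 1.75 | 0.45 | 0.66 | 32% |

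At n = 20 the loss is 21 to 33%. As an analytic check, a median split of a normal variable keeps 2/π = 64% of the information. A test with 80% power has z = 1.96 + 0.84 = 2.80; after the split, power is Φ(2.80 × √(2/π) − 1.96) = Φ(0.275) = 0.61, a loss of 24%. The 36% is a loss of information, not of power.

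**If the cut with the smallest p-value were chosen, with no true association.**
- Fisher, any cut in the middle half: about 13 to 15% at n = 31 and 25% response; about 9% at n = 20; about 7% at n = 31 and 10% response.
- Log-rank, n = 31: 15 to 16% with three quartile cuts, 21% over the 30th to 70th percentiles, 29 to 30% over the 20th to 80th, and 39 to 40% over the 10th to 90th.

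**The case against.** The best defence is Section 6.4.5. A reader might infer from Sections 6.3 and 6.4.2 that the mechanistic question is examined only through cut groups. It is not. The hypothesis is that hypoxia falls on treatment, and Section 6.4.5 analyses that change by paired tests and compares it between responders and non-responders by t or rank-sum test, all on uncut values. It also plans regression models for two of the four domains. This stands, and it narrows the point to marker level against response, and to PFS and OS, for hypoxia and immune phenotype.

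Other parts also stand:
- No section says that cuts will be chosen from the data; the text only leaves it open.
- The markers to be grouped are not named. A naturally categorical one, such as a positive or negative stain, loses nothing by grouping.
- Section 2.4 calls the work exploratory, and Section 6.4.4 makes its subgroup log-rank tests conditional on the number of events.

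What the defence does not supply is an uncut analysis for the remaining links, or a fixed cut for any grouped test.

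**Conclusion.** The point holds in limited form. For a quantitative marker at 25% response, n = 31 and an odds ratio of 3 to 4 per SD, the median split with Fisher's test costs about a third or more of the power of a rank-sum test, and about two thirds at an assumed n = 20. For log-rank against Cox the cost is about 20 to 33%, so a reader should not carry the Fisher figure over to PFS and OS.

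Nor should a reader infer a general tripling of false positives. Roughly three times nominal fits Fisher at n = 31 and 25% response with a search over the middle half. It is less at n = 20 or at 10% response, and for log-rank it runs from about three to eight times nominal (15% ÷ 5% to 40% ÷ 5%) according to the search range. All of this is conditional on a data-chosen cut, which the plan permits but does not propose.

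The sizes rest on a normal marker and assumed effects. The change should be made because a better analysis of the same data is available. It does not bear on the primary decision, whose stated 0.08 and 0.81 are unaffected.

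**What to change.** 1. In Sections 6.3, 6.4.2 and 6.4.4, analyse quantitative markers as continuous: a rank-sum test or single-marker logistic model for response, and a Cox model per SD for PFS and OS.
2. In Section 6.4.5, extend the logistic and Cox models to hypoxia and immune-infiltrate markers, and state that quantitative markers enter as continuous.
3. Keep grouped Fisher or log-rank tests only for naturally categorical markers, or for a median split fixed in advance and used for display.

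The cost is analysis-plan wording; no new data, patients or procedures are needed. The drawback is that the logistic and Cox models assume a log-linear effect of the marker. When to start the PFS and OS clock for a week-12 marker value is a separate question and is not part of this point.

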6.4.3 Safety Analysis (Secondary)

We will consider a toxicity event to be an adverse event (evaluated by CTCAE 5.0) that is possibly, probably, or definitely related to treatment. The maximum grade of toxicity for each category of interest will be recorded for each patient and the summary results will be tabulated by category and grade.

All adverse events occurring up to 28 days after the last intake of study medication will be recorded. These adverse events will be reported as listings and summarized as frequency tables by treatment group and the body system. Additional presentations will include summaries by severity and relationship to trial treatment.

Withdrawals of patients from study medication will be reported as listings and summary tables. All summaries and listings of adverse events and laboratory data will be based on the safety population.

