4.2.4 Starting Dose and Modifications

4.2.4.1 Nivolumah

The Nivolumab dose if 480 mg IV every 4 weeks.

Adverse events (both non-serious and serious) associated with nivolumab exposure may represent an immunologic etiology. These adverse events may occur shortly after the first dose or several months after the last dose of treatment. Nivolumab must be withheld for drug-related toxicities and severe or life-threatening AEs as per table 3 below. See Section 4.3.1 for supportive care guidelines, including use of corticosteroids.

At the end of the study period, Bristol-Myers Squibb Company will not continue to supply study drug to subjects/investigators unless the Sponsor-Investigator chooses to extend the study. The treating physician is responsible to ensure that the subject receives appropriate standard of care or other appropriate treatment.

No modifications in the dose of nivolumab are permitted. Dose delays are permitted, as outlined below.

Table 3: Nivolumab Dose Delay and Discontinuation Guidelines for Drug-Related Adverse Events

Toxicity	Hold Treatment for Grade	Timing for Restarting Treatment	Treatment Discontinuation
Diarrhea/Colitis	2-3	Toxicity resolves to Grade 0-1	Toxicity does not resolve within 12 weeks of last dose or inability to reduce corticosteroid to 10 mg or less of prednisone or equivalent per day within 12 weeks

Toxicity	Hold Treatment for Grade	Timing for Restarting Treatment	Treatment Discontinuation
	4	Permanently discontinue	Permanently discontinue
AST, ALT, or Increased	2	Toxicity resolves to Grade 0-1	Toxicity does not resolve within 12 weeks of last dose
Bilirubin	3-4	Permanently discontinue (see exception below) ^a	Permanently discontinue
Type 1 diabetes mellitus (if new onset) or Hyperglycemia	T1DM or 3-4	Hold for new onset Type 1 diabetes mellitus or Grade 3-4 hyperglycemia associated with evidence of beta cell failure	Resume when patients are clinically and metabolically stable
Hypophysitis	2-4	Toxicity resolves to Grade 0-1. Therapy with can be continued while endocrine replacement therapy is instituted	Toxicity does not resolve within 12 weeks of last dose or inability to reduce corticosteroid to 10 mg or less of prednisone or equivalent per day within 12 weeks
Hyperthyroidism	3	Toxicity resolves to Grade 0-1	Toxicity does not resolve within 12 weeks of last dose or inability to reduce corticosteroid to 10 mg or less of prednisone or equivalent per day within 12 weeks

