5.1.2.1 Adverse Event (AE) Monitoring

The investigator or qualified designee will assess each subject to evaluate for potential new or worsening AEs as specified in the Trial Flow Chart and more frequently if clinically indicated. Adverse experiences will be graded and recorded throughout the study and during the follow-up period according to NCI CTCAE Version 5.0 (see Section 11.2). Toxicities will be characterized in terms regarding seriousness, causality, toxicity grading, and action taken with regard to trial treatment.

Please refer to section 7.2 for detailed information regarding the assessment and recording of AEs.

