5.2 Assessing and Recording Adverse Events

An adverse event is defined as any untoward medical occurrence in a patient or clinical investigation subject administered a pharmaceutical product and which does not necessarily have to have a causal relationship with this treatment. An adverse event can therefore be any unfavorable and unintended sign (including an abnormal laboratory finding, for example), symptom, or disease temporally associated with the use of a medicinal product or protocol-specified procedure, whether or not considered related to the medicinal product or protocol-specified procedure. Any worsening (i.e., any clinically significant adverse change in frequency and/or intensity) of a preexisting condition that is temporally associated with the use of the treatments agents, is also an adverse event.

All adverse events that occur after the consent form is signed but before treatment allocation/randomization must be reported by the investigator if they cause the subject to be excluded from the trial, or are the result of a protocol-specified intervention, including but not limited to washout or discontinuation of usual therapy, diet, placebo treatment or a procedure.

From the time of treatment allocation/randomization through 100 days following cessation of treatment, or until the participant initiates new anticancer therapy, whichever is earlier, all adverse events must be reported by the investigator. Such events will be recorded at each examination on the Adverse Event case report forms/worksheets. The reporting timeframe for adverse events meeting any serious criteria is described in section 7.2.3.1. The investigator will make every attempt to follow all subjects with non-serious adverse events for outcome.

Adverse events will not be collected for subjects during the pre-screening period (for determination of archival tissue status) as long as that subject has not undergone any protocol-specified procedure or intervention. If the subject requires a blood draw, fresh tumor biopsy etc., the subject is first required to provide consent to the main study and AEs will be captured according to guidelines for standard AE reporting.

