The Sponsor will reconcile the clinical database SAE cases (case level only) transmitted to BMS Global Pharmacovigilance ([contact]). Frequency of reconciliation should be every 3 months and prior to the database lock or final data summary. BMS GPV&E will email, upon request from the Investigator, the GPV&E reconciliation report. Requests for reconciliation should be sent to [contact]. The data elements listed on the GPV&E reconciliation report will be used for case identification purposes. If the Investigator determines a case was not transmitted to BMS GPV&E, the case should be sent immediately to BMS.

Refer to Table 3 in Section 4.2.4 for additional details regarding each of the above criteria.

For the time period following the subject's written consent to participate in the study through 100 days of discontinuation of dosing, any serious adverse event, or follow up to a serious adverse event, including death due to any cause other than progression of the cancer under study (reference Section 7.2.3.3 for additional details) that occurs to any subject must be reported within 24 hours to the Sponsor and within 24 hours or 1 business day to BMS and Pfizer Global Safety if it causes the subject to be excluded from the trial, or is the result of a protocol-specified intervention, including but not limited to washout or discontinuation of usual therapy, treatment or a procedure.

For the time period beginning at treatment allocation/randomization through 100 days following cessation of treatment with nivolumab, or until the participant initiates new anticancer therapy, whichever is earlier, any serious adverse event, or follow up to a serious adverse event, including death due to any cause other than progression of the cancer under study (reference Section 7.2.3.3 for additional details), whether or not related to study treatment, must be reported within 24 hours to the Sponsor and within 24 hours or 1 business day to BMS and Pfizer Global Safety.

Additionally, any serious adverse event, considered by an investigator who is a qualified physician to be related to treatment that is brought to the attention of the investigator at any time following consent through the end of the specified safety follow-up period specified in the paragraph above, or at any time outside of the time period specified in the previous paragraph also must be reported immediately to the Sponsor and to BMS and Pfizer Global Safety.

REPORTING OF SERIOUS ADVERSE EVENTS

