6.4 Statistical Analysis Plan

6.4.1 Analysis Sets

DLT evaluable patients are study-eligible patients (i.e., those meeting all of the protocol inclusion/exclusion criteria) who have finished one cycle of the regimen without a DLT, and those who received at least one dose of the regimen and experienced DLT in the first cycle.

Response evaluable patients are study-eligible patients (i.e., those meeting all of the protocol inclusion/exclusion criteria) who have received the regimen and stayed on study long enough for at least one follow-up of response. Patients who didn't come back for scan but clinically progressed will also be considered as evaluable for response, and the best response for these patients is progressive disease.

Safety population - all study eligible patients who received any dose of the study drug will be included in the safety population.

Efficacy population - the data from all treated patients will be used in the intent to treat analyses of tumor response and survival (progression-free and overall). Patients who complete at least one cycle of the treatment will be included in the per-protocol analysis of bioactivity endpoint. Patients who are considered non-compliant are not evaluable for the per-protocol analysis of the primary efficacy endpoint, but still evaluable for safety analysis, so they will be replaced for the primary efficacy analysis.

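### Section 6.4.3 tabulates adverse events to 28 days after last intake, but Section 5.2 requires them to 100 days or new therapy; the safety set also drops dosed patients found ineligible

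*Combined protocol and SAP*

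**What the plan says.** **Window.** Section 6.4.3 says: "All adverse events occurring up to 28 days after the last intake of study medication will be recorded". Its next sentence makes those events the content of the listings and of the frequency tables by body system, with further summaries by severity and relationship. The first paragraph of 6.4.3 also describes a table of maximum grade per patient, restricted to events at least possibly related to treatment, and gives no time limit for it.

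Section 5.2 sets a different period for all adverse events: "From the time of treatment allocation/randomization through 100 days following cessation of treatment, or until the participant initiates new anticancer therapy", whichever comes first. Section 5.1.2.1 adds: "Adverse experiences will be graded and recorded throughout the study and during the follow-up period".

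Section 5.2.2.1 gives two periods for serious events. One runs "through 100 days of discontinuation of dosing, any serious adverse event"; the other runs "through 100 days following cessation of treatment with nivolumab, or until the participant initiates new anticancer therapy, whichever is earlier".

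On late onset, Section 4.2.4.1 says of nivolumab: "These adverse events may occur shortly after the first dose or several months after the last dose of treatment".

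**Population.** Section 6.4.1 says that "all study eligible patients who received any dose of the study drug will be included in the safety population", having defined study-eligible earlier in the same section as meeting every inclusion and exclusion criterion. Section 6.4.3 bases all adverse event and laboratory output on that set. For efficacy, Section 6.4.1 says that "the data from all treated patients will be used in the intent to treat analyses of tumor response and survival", with no eligibility condition. Non-compliant patients stay evaluable for safety.

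**The concern.** Safety is the first secondary objective (Section 2.4). Read literally, 6.4.3 stops recording and tabulating at day 28, although 5.2 obliges the investigator to keep reporting to day 100. Two things could follow.

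- Staff working from 6.4.3 could stop recording at day 28. Events never recorded may not be recoverable at analysis.
- If the events are collected as 5.2 requires, the general listings and tables would still leave them out. Late events judged unrelated would then have no stated output at all.

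The omitted period is one in which the protocol itself expects nivolumab events. Section 4.2.5 adds that late toxicity will be weighed in choosing a final dose and schedule if the combination is developed further.

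The population rule is a separate weakness. A patient who was dosed and later found ineligible contributes to response and survival but to no safety summary.

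**Working it through.** The plan gives no figure to reproduce on this point. The check sets the texts side by side and then does simple arithmetic.

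**1. The texts compared**

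| Section | Events covered | End of window | Clock starts at |
|---|---|---|---|
| 6.4.3, listings and tables | all adverse events | day 28 | last intake of study medication |
| 6.4.3, maximum-grade table | related events, worst grade per patient | not stated | not stated |
| 5.2 | all adverse events | day 100 or new anticancer therapy, whichever is earlier | cessation of treatment |
| 5.2.2.1 | serious events | day 100; in one of its two statements also capped at new therapy | discontinuation of dosing, or cessation of nivolumab |

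Nothing describes the 28 days as an analysis cut within a longer collection period. Because 6.4.3 speaks of what will be recorded, it conflicts with 5.2 on collection as well as on tabulation. The clock matters because the two drugs have separate discontinuation rules (Tables 3 and 4), so they can stop on different dates.

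**2. Size of the window gap**

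Let *t* be the day on which new anticancer therapy starts, counted from the end of treatment with both drugs stopped on the same day.

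Days required by 5.2 but outside the 6.4.3 tables = max(0, min(*t*, 100) − 28):

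- *t* = 28: 0
- *t* = 42: 42 − 28 = 14
- *t* = 60: 60 − 28 = 32
- no new therapy by day 100: 100 − 28 = 72

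Days inside 6.4.3 but beyond the general 5.2 window = max(0, 28 − *t*):

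- *t* = 14: 14
- *t* = 7: 21
- *t* = 1: 27

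**3. What the gap could hold**

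The documents give neither the timing nor the rate of post-treatment events, so the inputs below are assumptions.

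*Timing.* Suppose post-treatment events have exponential onset with median *m* days, and there is no new therapy. The share of events to day 100 that fall after day 28 is [F(100) − F(28)] / F(100), with F(*x*) = 1 − 2^(−*x*/*m*):

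- *m* = 14: 24.5%
- *m* = 28: 45.4%
- *m* = 60: 59.7%
- *m* = 90: 63.9%
- uniform onset: 72/100 = 72%

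*Patients.* Take the planned 31 (Section 6.3). Let *q* be the proportion free of new therapy to day 100, and *p* the proportion of those with an event in days 29 to 100. The expected number with an omitted event is 31 × *q* × *p*:

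- *q* = 0.25, *p* = 0.05: 0.39
- *q* = 0.50, *p* = 0.10: 1.55
- *q* = 1, *p* = 0.20: 6.2

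This formula gives no weight to patients who start new therapy between days 28 and 100, although step 2 shows that they lose days too.

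**4. Population**

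The number of dosed ineligible patients is not given. One, two or three of them are 1/31 = 3.2%, 2/31 = 6.5% or 3/31 = 9.7% of the trial. Dropping one patient changes an assumed event proportion *x*/31 to (*x* − 1)/30 if that patient had the event, or *x*/30 if not:

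| Assumed proportion | Dropped patient had event | Did not |
|---|---|---|
| 3/31 = 9.7% | 2/30 = 6.7% | 3/30 = 10.0% |
| 9/31 = 29.0% | 8/30 = 26.7% | 9/30 = 30.0% |
| 15/31 = 48.4% | 14/30 = 46.7% | 15/30 = 50.0% |

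Dropping three from 9/31 gives between 6/28 = 21.4% and 9/28 = 32.1%.

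**The case against.** The strongest defence is that little of importance is lost.

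- **Late immune-mediated events judged related still reach the maximum-grade table, which has no window.** This stands, and it limits the harm. That table shows only the worst grade per patient and only related events, so it does not replace the listings or cover unrelated events.
- **Oversight continues past day 28.** Serious events are reportable to day 100 or new therapy, case reconciliation runs every 3 months (Section 5.2.2.1), and the monthly meetings review serious events (Section 8.1). This stands for oversight. It does not put the events into the planned safety analysis.
- **Day 28 matches the week-4 visit, the only in-person follow-up visit stated in Section 4.5; the flow chart footnote calls the day-100 contact survival follow-up, which may be by phone.** A deliberate cut is therefore plausible, but the text does not state one, and 5.2 would still contradict it. The point does mean that data for days 29 to 100 may be gathered less systematically.
- **Section 5.2 has no single window of its own.** Under 5.2.2.1, related serious events are reportable at any time. Under 5.2.2.2, events of clinical interest run to 100 days, or to 30 days after treatment stops if new therapy begins. This is true and the fix must allow for it, but it does not remove the conflict over general adverse events.
- **The patient counts rest on assumed rates.** They do, and they also presume full enrolment. A stop after the 16 first-stage patients would scale them by 16/31, to between 16 × 0.25 × 0.05 = 0.2 and 16 × 1 × 0.20 = 3.2.
- **Dosed ineligible patients should be rare**, since eligibility is reviewed before entry (Section 5.1.1.2) and must be complete before the baseline biopsy (flow chart footnote d). This is accepted.

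**Conclusion.** Both points hold as written. The contradiction between 6.4.3 and 5.2 is certain, because it rests on the text alone. Its reach is 72 post-treatment days for a patient with no new therapy by day 100, fewer if new therapy starts between days 28 and 100, and up to 27 days in the opposite direction if it starts before day 28. How many events this involves is unknown; 0.4 to 6.2 patients is an illustration, not an estimate from trial data.

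The population restriction affects only dosed patients found ineligible. Its direction is unknown and such patients should be few, so it adds little weight beyond the inconsistency with the efficacy set.

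Sample size, type I error, power and the primary decision rule do not change, and the stopping rules in Section 6.2 refer to neither this window nor this set. This should be corrected because it would leave the safety tables incomplete. It is not a threat to the primary conclusion.

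**What to change.** In Section 6.4.3:

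- Replace the 28-day sentence so that recording, listings and tables all cover every adverse event that 5.2 requires to be reported.
- State one reference date for patients who stop nivolumab and axitinib on different dates, and use it in 5.2 and 5.2.2.1 as well.
- Say how events after new therapy that starts before day 28 are handled, for example kept and flagged.
- Say how events reportable only under 5.2.2.1 or 5.2.2.2, outside the general window, are shown. A separate listing would keep one window for the main tables.
- State the window of the maximum-grade table.

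In Section 6.4.1, define the safety population as all patients who received any dose of nivolumab or axitinib, regardless of eligibility.

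The cost is wording and somewhat more tabulation, since 5.1.2.1 and 5.2 already require the data. The day-100 contact should be described as including an adverse event enquiry, which may add some site work. One downside needs attention: a strict 5.2 window would shorten the tables by up to 27 days for patients who start new therapy before day 28, unless the text keeps those events.
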